7.0 CORRELATIVE STUDIES

Collection of tissue specimen

At the time expander-implant exchange, a portion of the capsule is normally excised as part of the standard of care. For research purposes, we will collect and study several small pieces of capsular tissue excised at the time of surgery. The tissue collected will be used to determine if zafirlukast can reduce the thickness and scarring of the capsule tissue compared to standard of care.

Handling of specimen

Tissue samples will be fixed in 10% neutral-buffered formalin and embedded in paraffin for further analysis.

Shipping of specimen

Specimen will be processed by the surgical pathology department laboratory affiliated with UCSF.

8 ADVERSE EVENTS

8.1 Adverse Event (AE) Monitoring

The investigator or qualified designee will assess each subject to evaluate for potential new or worsening AEs and more frequently if clinically indicated. Adverse experiences will be assessed, graded and recorded throughout the study and during the follow-up period by the treating physician. Toxicities will be characterized in terms regarding seriousness, causality, toxicity grading, and action taken with regard to trial treatment.

8.2 Definition of Adverse Event

An adverse event (also known as an adverse experience) is defined as any untoward medical occurrence associated with the use of a drug in humans, whether or not considered drug related. More specifically, an adverse event can be any unfavorable and unintended sign (e.g., an abnormal laboratory finding), symptom, or disease temporally associated with the use of a drug, without any judgment about causality. An adverse event can arise from any use of the drug (e.g., off-label use, use in combination with another drug) and from any route of administration, formulation, or dose, including an overdose.

8.3 Adverse reaction

An adverse reaction is defined as any adverse event caused by the use of a drug. Adverse reactions are a subset of all suspected adverse reactions for which there is reason to conclude that the drug caused the event.

8.3.1 Suspected

A suspected adverse reaction is defined as any adverse event for which there is a reasonable possibility that the drug caused the adverse event. For the purposes of IND safety reporting, "reasonable possibility" indicates that there is evidence to suggest a causal relationship between the drug and the adverse event. A suspected adverse reaction implies a lesser degree of certainty about causality than an adverse reaction.

8.3.2 Unexpected

An adverse event or suspected adverse reaction is considered unexpected if it is not listed in the investigator brochure or package insert(s), or is not listed at the specificity or severity that has been observed, or, if an investigator brochure is not required or available, is not consistent with the risk information described in the general investigational plan or elsewhere in the current application.

“Unexpected,” as used in this definition, also refers to adverse events or suspected adverse reactions that are mentioned in the investigator brochure as occurring with a class of drugs or as anticipated from the pharmacological properties of the drug, but are not specifically mentioned as occurring with the particular drug under investigation.

Adverse events that would be anticipated to occur as part of the disease process are considered unexpected for the purposes of reporting because they would not be listed in the investigator brochure. For example, a certain number of non-acute deaths in a cancer trial would be anticipated as an outcome of the underlying disease, but such deaths would generally not be listed as a suspected adverse reaction in the investigator brochure.

Some adverse events are listed in the Investigator Brochure as occurring with the same class of drugs, or as anticipated from the pharmacological properties of the drug, even though they have not been observed with the drug under investigation. Such events would be considered unexpected until they have been observed with the drug under investigation. For example, although angioedema is anticipated to occur in some patients exposed to drugs in the ACE inhibitor class and angioedema would be described in the investigator brochure as a class effect, the first case of angioedema observed with the drug under investigation should be considered unexpected for reporting purposes.

8.3.3 Serious

An adverse event or suspected adverse reaction is considered serious if, in the view of the study PI, it results in any of the following outcomes:

- Death
- Life-threatening adverse event
- Inpatient hospitalization or prolongation of existing hospitalization
- A persistent or significant incapacity or substantial disruption of the ability to conduct normal life function
- Congenital anomaly/birth defect

Important medical events that may not result in death, are life-threatening, or require hospitalization may be considered serious when, based upon appropriate medical judgment, they may jeopardize the patient or subject and may require medical or surgical intervention to prevent one of the outcomes listed in this definition. Examples of such medical events include allergic bronchospasm requiring intensive treatment in an emergency room or at home, blood dyscrasias or convulsions that do not result in inpatient hospitalization, or the development of drug dependency or drug abuse.

8.3.4 Life-threatening

An adverse event or suspected adverse reaction is considered life-threatening if, in the view of either the study Principal Investigator, its occurrence places the patient or subject at immediate risk of death. It does not include an adverse event or suspected adverse reaction that, had it occurred in a more severe form, might have caused death.

8.4 Evaluation of an Adverse Event

All grade 3 and above adverse events will be entered into OnCore®, whether or not the event is believed to be associated with use of the study drug.

The Investigator will assign attribution of the possible association of the event with use of the investigational drug, and this information will be entered into OnCore® using the classification system listed below:

Relationship	Attribution	Description
Unrelated to investigational drug/intervention	Unrelated	The AE is clearly NOT related to the intervention
	Unlikely	The AE is doubtfully related to the intervention
Related to investigational drug/intervention	Possible	The AE may be related to the intervention
	Probable	The AE is likely related to the intervention
	Definite	The AE is clearly related to the intervention

Signs or symptoms reported as adverse events will be graded and recorded by the Investigator according to the CTCAE. When specific adverse events are not listed in the CTCAE they will be graded by the Investigator as none, mild, moderate or severe according to the following grades and definitions:

- Grade 0 No AE (or within normal limits)
- Grade 1 Mild; asymptomatic or mild symptoms; clinical or diagnostic observations only; intervention not indicated
- Grade 2 Moderate; minimal, local, or noninvasive intervention (e.g., packing, cautery) indicated; limiting age-appropriate instrumental activities of daily living (ADL)
- Grade 3: Severe or medically significant but not immediately life-threatening; hospitalization or prolongation of hospitalization indicated; disabling; limiting self-care ADL
- Grade 4: Life-threatening consequences; urgent intervention indicated
- Grade 5: Death related to AE

8.4.1 NCI Common Terminology for Adverse Events (CTCAE)

An investigator who is a qualified physician will evaluate all adverse events according to the NCI Common Terminology for Adverse Events (CTCAE), version 4.0. Any adverse event which changes CTCAE grade over the course of a given episode will have each change of grade recorded on the adverse event case report forms/worksheets.

All adverse events regardless of CTCAE grade must also be evaluated for seriousness.

8.5 Follow-up of Adverse Events

All adverse events will be followed with appropriate medical management until resolved. Patients removed from study for unacceptable adverse events will be followed for 30 days or until resolution or stabilization of the adverse event. For selected adverse events for which administration of the investigational drug was stopped, a re-challenge of the subject with the investigational drug may be conducted if considered both safe and ethical by the Investigator.

8.6 Adverse Events Reporting

All adverse events, whether or not unexpected, and whether or not considered to be associated with the use of the study drug, will be entered into OnCore®, as noted above.

The Investigator will assess all adverse events and determine reportability requirements to the UCSF Data and Safety Monitoring Committee (DSMC) and UCSF's Institutional Review Board, the Committee on Human Research (CHR); and, when the study is conducted under an Investigational New Drug Application (IND), to the Food and Drug Administration (FDA) if it meets the FDA reporting criteria.

All adverse events entered into OnCore® will be reviewed by the Helen Diller Family Comprehensive Cancer Center Site Committee on a weekly basis. The Site Committee will review and discuss at each weekly meeting the selected toxicity, the toxicity grade, and the attribution of relationship of the adverse event to the administration of the study drug(s).

All grade(s) 3-5 adverse events entered into OnCore® will be reviewed on a monthly basis at the Site Committee meetings. The Site Committee will review and discuss the selected toxicity, the toxicity grade, and the attribution of relationship of the adverse event to the administration of the study drug(s).

In addition, all suspected adverse reactions considered "serious" entered into OnCore®, will be reviewed and monitored by the Data and Safety Monitoring Committee on an ongoing basis and discussed at DSMC meetings, which take place every six weeks.

8.7 Expedited Reporting

Reporting to the Data and Safety Monitoring Committee

If a death occurs during the treatment phase of the study or within 30 days after the last administration of the study drug(s) and it is determined to be related either to the study drug(s) or to a study procedure, the Investigator or his/her designee must notify the DSMC Chair (or qualified alternate) within 1 business day of knowledge of the event. The contact may be by phone or e-mail.

Reporting to UCSF Committee on Human Research (Institutional Review Board)

The Principal Investigator must report events meeting the UCSF CHR definition of "Unanticipated Problem" (UP) within 10 business days of his/her awareness of the event.

9.0 STATISTICAL CONSIDERATIONS AND EVALUATION OF RESULTS

Determination of sample size and accrual rate

Sample size calculated to be 82 (41 per arm) based on a two-tailed alpha of 0.05, with a beta of 0.18. With a possible 10% attrition rate, the sample size is increased to 90 (45 per arm). As approximately 60 patients undergo mastectomy with immediate tissue expander placement per year at Mt. Zion, it is expected that roughly 80% of these women will be enrolled in the study.

The determination of sample size is based on the assumption that treatment with the leukotriene inhibitor zafirlukast will decrease capsule thickness in women with tissue expanders at the time of implant exchange. Based on the reported results from literature review, a capsule thickness of >2.4mm would be considered undesirable and <1.2mm would be considered desirable. We assume the capsule thickness is <1.2mm under zafirlukast as the target efficacy of clinical importance for the study population and an efficacy of 50% reduction in capsule contracture between two cohorts would be considered clinically meaningful. Under the t-test with a 2-sided alpha of 5%, we will need 45 evaluable patients in each cohort to have >80% power to detect an

improvement in capsule thickness from average 2.4mm (sd 2mm) to average 1.2mm (sd 2mm). Specifically, the study hypothesis is defined as:

H0: $\mu_1 \geq \mu_0$ (The capsule thickness of the cohort A is greater than capsule thickness of the cohort B versus

H1: $\mu_1 < \mu_0$ (The capsule thickness of the cohort A is greater than capsule thickness of the cohort B.

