3.2 Number of Subjects

90 total: 45 per cohort factoring in a 10% attrition rate

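### Section 9.0 does not deliver its stated power: 41 per arm gives about 77%, not 82%, and the 45 evaluable per arm needed for 80% are the 45 enrolled before attrition

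*Combined protocol and SAP*

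**What the plan says.** Section 9.0 gives two sample sizes for one design.

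- The first: "Sample size calculated to be 82 (41 per arm) based on a two-tailed alpha of 0.05, with a beta of 0.18". The total is then raised to 90 (45 per arm) for a possible 10% attrition. This sentence carries no effect size or SD of its own.
- The second, in the next paragraph, assumes a two-sided 5% t-test and mean thickness of 2.4 versus 1.2 mm with SD 2 mm in each cohort: "we will need 45 evaluable patients in each cohort to have >80% power".

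Section 3.2 makes clear that 45 is the enrolled number with losses already allowed for: "90 total: 45 per cohort factoring in a 10% attrition rate". Section 6.3 closes enrolment at 90 (45 per cohort). Section 9.1 names t-tests for the primary endpoint and says that missing data will not be imputed.

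Section 9.0 then writes the hypotheses in one-sided symbols, H0: μ1 ≥ μ0 and H1: μ1 < μ0. Both carry the same gloss: "The capsule thickness of the cohort A is greater than capsule thickness of the cohort B".

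**The concern.** The number 45 does two jobs that exclude each other. It is the enrolled number that shrinks to about 41 after losses, and it is also the evaluable number that must remain after losses. If 45 evaluable are needed, enrolling 45 with 10% attrition is too few. If 41 evaluable are enough, the second statement is wrong.

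The quoted type II error of 18% also looked too small for 41 per arm at a standardised difference of 0.6. What is at stake is how the trial is judged. A reader or review committee would take 18% as the chance of missing the target effect, and would give a null result more weight against zafirlukast than the design supports. In addition, the words beside H1 state the opposite of the intended claim.

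**Working it through.** **Inputs.** From Section 9.0: means 2.4 and 1.2 mm, so δ = 1.2 mm; SD σ = 2 mm in both arms; two-sided α = 0.05; attrition 10%. From Section 3.1: 1:1 allocation. From Section 9.1: t-test, no imputation. The standardised difference is d = 1.2/2 = 0.60.

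**Formula.** For n evaluable per arm, the two-sample t statistic has 2n − 2 degrees of freedom and noncentrality λ = δ / (σ√(2/n)). Power is the probability that a noncentral t with that λ falls outside ±t(0.975, 2n − 2). The normal approximation is Φ(λ − 1.96).

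**First statement (41 per arm, 82% power).** λ = 1.2 / (2√(2/41)) = 2.717 and the critical t on 80 df is 1.990. Power is 76.5%. The normal approximation gives Φ(2.717 − 1.960) = 77.5%. The stated 82% is not reproduced by either route.

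**Second statement (45 evaluable per arm, more than 80%).** λ = 2.846, critical t on 88 df = 1.987, power 80.4% (normal approximation 81.2%). This reproduces.

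| Evaluable per arm | t-test power | Normal approximation |
|---|---|---|
| 40 | 75.5% | 76.5% |
| 40.5 | 76.0% | 77.0% |
| 41 | 76.5% | 77.5% |
| 44 | 79.5% | 80.4% |
| 45 | 80.4% | 81.2% |
| 46 | 81.2% | 82.1% |
| 47 | 82.1% | 82.9% |

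By t-test, 45 is the smallest whole number that reaches 80%, and 47 the smallest that reaches 82%.

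**Evaluable patients at the planned size.** 45 × 0.9 = 40.5 per arm. Power there is 76.0%, so the type II error is 24.0%; at 41 per arm it is 23.5%. The plan states 18%.

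**Could another reading rescue the 82%?**
- One-sided 5% at 41 per arm gives 85.3%, which overshoots. Both alpha statements say two-sided in any case.
- Reaching 82% at 41 per arm with a two-sided test needs d of about 0.643. That means an SD of 1.2/0.643 = 1.87 mm, or a difference of 0.643 × 2 = 1.29 mm. Neither figure is in the documents.

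**Attrition step.** 82 × 1.1 = 90.2, which matches the 90 in the plan. Allowing for a 10% loss requires division: 82/0.9 = 91.1, so 92. This is a difference of one patient per arm.

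**Enrolment needed for the stated targets.** 45/0.9 = 50 per arm (100 total) for 80% power; 47/0.9 = 52.2, so 53 per arm (106 total), for 82%.

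**The case against.** The strongest reply is that the 41-per-arm sentence states no effect or SD, so the 76.5% borrows its inputs from the next paragraph. An SD printed as 2 mm could be a rounded 1.87, and the targets are partly written as inequalities (below 1.2 mm, above 2.4 mm), which leaves room for a slightly larger difference. At SD 1.87 mm, 40.5 per arm would give 81.4%. It is true that the source of the 82% cannot be traced. But nothing in the text supports another SD, and this reading breaks the second statement: at SD 1.87 mm the same formula gives 80.9% at 40 per arm, so 45 evaluable would not be needed. No single set of inputs makes 41 per arm give 82% and also makes 45 per arm the number needed for 80%.

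The second reply is that the shortfall is small, depends on attrition that the plan calls only possible, and is smaller than the uncertainty in the SD (1.9 instead of 2.0 mm moves power at 41 per arm from 76.5% to 80.7%). A completed trial is also read mainly from its confidence interval, which Section 9.1 provides. This is fair about the practical consequence and limits how much should be made of the point. It does not remove a contradiction in the primary sample-size justification.

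The third reply is that the side points are minor, and that is accepted. The attrition multiplier moves the total by two patients. Directional hypotheses alongside a two-sided test are a common convention. The gloss on H1 is evidently a copying slip, since the symbols and the surrounding text show the intended direction. These should be corrected in the same edit, but the finding does not rest on them.

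**Conclusion.** The concern holds. On the plan's stated inputs, 41 per arm gives about 77% power rather than 82%, and the 45 evaluable per arm that would give 80.4% are not available once 10% of the 45 enrolled per arm are lost. At the planned size and attrition, power is about 76% and the type II error about 24%, against a stated 18%.

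This rests on a difference of 1.2 mm, SD 2 mm, a two-sided 5% t-test, equal arms, and lost patients contributing nothing to the primary comparison. It also assumes that the final test keeps the full 5%. The efficacy interim at one year in Section 9.1 has no stated alpha adjustment, and any adjustment would lower power slightly further.

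**What to change.** Keep 90 randomised and replace the two statements in Section 9.0 with one, for example: *90 patients (45 per arm) will be randomised. Allowing for 10% attrition, about 40 per arm will be evaluable, giving about 76% power to detect 2.4 versus 1.2 mm (SD 2 mm) with a two-sided 5% t-test; power is 80% only if all 45 per arm are evaluable.* Remove the beta of 0.18 and the requirement for 45 evaluable, and bring the synopsis and Section 3.2 into line.

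State the hypotheses to match the test, H0: μ1 = μ0 and H1: μ1 ≠ μ0, with words that agree with the symbols.

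The cost is wording and a less favourable stated power, with no extra patients. If the sponsor prefers to keep the target of more than 80%, enrolment has to rise to 50 per arm (100 total). The accrual figures in the plan (60 per year × 80% × 2 years = 96) fall just short of that, so the two-year enrolment period would need to be slightly longer.

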9.1 Analyses Plans

This is an intention to treat analysis. All patients who were randomized will be evaluated.

Data will be summarized using descriptive statistics by study cohorts. For continuous variables, descriptive statistics will include the number of non-missing values, mean, standard deviation, median, minimum and maximum. For categorical variables, descriptive statistics will include counts and percentages per category by study cohorts.

Primary analysis:

The primary objective of the trial is to determine the capsule contracture between the two study cohorts and the primary efficacy outcome in this trial is capsule thickness at the time of expander-implant exchange. Capsule thickness will be determined by averaging thickness from three separate specimens per patient. The capsule thickness will be analyzed by study cohorts, and t-tests and descriptive statistics with mean, standard deviation and 95% confidence intervals will be used for significance. Missing data will not be imputed. An alpha level of 0.05 will be considered significant for the primary endpoint. For exploratory analysis, the primary endpoint of capsule thickness will be presented as mean \pm SEM and evaluated using analysis of variance (ANOVA) with factors including study cohort, radiotherapy and length of drug treatment.

Secondary Analysis:

For secondary objectives of the trial, we will determine the level of fibrosis and presence of collagen from the biopsy specimens. The level of fibrosis and the presence of collagen will be analyzed descriptively as continuous levels and as ordinal levels with mean, standard deviation and 95% confidence intervals. The difference in the level of fibrosis and relative presence of collagen between study cohorts will be compared using t-tests for significance.

Similar statistical methods will also be employed to analyze the capsule tissue that is removed at the time of expander-implant exchange to determine the level and presence of collagen, fibroblasts and myofibroblasts.

Confounding Factors:

In addition to primary and secondary analysis, we will also determine if there are other confounding factors such as variables in time and length treated with zafirlukast and radiation therapy by using ANOVA models on capsule thickness. Univariate analysis will be done on capsule thickness with all potential factors and selected variables of interest deemed significant will be further analyzed for interaction effect. Capsule thickness will be reported per subgroup of patients to account for time and radiation variables.

Other analysis:

An interim analysis is planned at 1 year to assess treatment efficacy in the treatment group compared to standard of care group.

